5.5.1.2. Treatment-emergent Exposure Durations

For estimating the average annualized event rates of treatment-emergent adverse events of special interest (Section 5.5.2.2 and 5.5.2.3), the treatment-emergent (TE) exposure durations (in days) of individual participants are required and calculated as [EOT+ 3 days] – Day 1 + 1 day. The TE exposure duration in months is calculated as (duration in days / 30.4) and in years (also called TE subject-years) as (duration in days / 365.25). The total TE exposure duration of a treatment group is the sum over individual participants of that treatment group, and the average TE exposure duration is the total duration divided by the number of participants of that treatment group.

For prostacyclin associated reactions (Section 5.5.2.3), additional TE exposure durations of individual participants are defined for the titration and maintenance periods.

- The TE exposure duration of the titration period will be calculated as:
 - If the participant did NOT prematurely stop the study intervention before Day 86: TE exposure duration (days) = 86.
 - If the participant prematurely stopped the study intervention before Day 86: TE exposure duration (days) = [EOT+ 3 days] – [Day 1] + 1 (Section 5.1.3).
- The TE exposure duration of the maintenance period will be calculated as:

- If the participant did NOT prematurely stop the study intervention before Day 86: TE exposure duration (days) = {[EOT +3 days] – [Day 1] + 1} – 86 (Section 5.1.3).
- If the participant prematurely stopped the study intervention before Day 86: TE exposure duration will not be calculated, and the participant will be excluded from the denominator.

For a period (titration or maintenance) the TE subject-years of individual participants are calculated as (period-specific duration in days / 365.25). The total TE subject-years for a period of a treatment group is the sum over individual participants included in the respective period of that treatment group.

5.5.2. Adverse Events

Any events recorded on the AE pages of the A303 CRF or A302 CRF.

5.5.2.1. Treatment-Emergent Adverse Events

Definition: The verbatim terms used in the CRF by investigators to identify adverse events will be coded using the MedDRA, version 22.0. Any AE occurring at or after the initial administration of study intervention (on Day 1 in STS [A302+A303] or OLS – see Section 5.1.2) through EOT plus 3 days is considered as treatment emergent (TE). If the event occurs on the day of the initial administration of study intervention, and either event time or time of administration are missing, then the event will be assumed to be treatment emergent. If the event date is recorded as completely missing, then the event will be considered as treatment emergent unless it is known to be prior to the first administration of study intervention based on partial onset date or resolution date. All reported treatment-emergent adverse events (TE-AEs) will be included in the analysis.

Population: All participants included in the STS (A302+A303) and OLS

Study Intervention: Selexipag

Outcome measures: Binary variables, occurrence for each of the following categories of TE-AEs, TE-SAEs and SAEs (Yes/No):

- All TE-AEs
- TE-Serious AEs (TE-SAEs), including fatal (by the tick box 'Yes' for 'Serious' in CRF)
- All SAEs occurring at or after the initial administration of study intervention through EOT plus 30 days (instead of plus 3 days as for TE-SAEs)
- TE-AEs leading to discontinuation of study intervention (by the tick box 'Permanently discontinued' for 'Action taken with study drug' in CRF)
- TE-AEs by severity (by 'Maximum intensity' in CRF)
- TE-AEs by relationship to study intervention (defined as 'Related' or 'Unrelated' in CRF)
- TE-AEs leading to fatal outcome (by the tick box 'Death' for 'Outcome' in CRF)
- TE-AEs and TE-Serious AEs associated with COVID-19 infection.

- TE-AEs associated with COVID-19 infection leading to fatal outcome.

Summary method(s) for outcome measure:

- The (crude) incidence proportion defined as the percentage of participants who experienced at least 1 occurrence of a specific AE divided by the total number of participants.
- All categories of TE-AEs will be summarized by SOC and PT, whereby the PT “Disease Progression” is only reported, if it is the only PT that the respective AE is coded to. The categories of All TE-AEs, TE-SAEs and SAEs will also be summarized by PT. An overall summary of all TE-AE categories will be provided. This will include the TE-AEs associated with COVID-19 infection. TE-AEs associated with COVID-19 infection will be reported for OLS only.
- The exposure-adjusted incidence rate (EAIR) will be summarized by SOC and PT. TE-EAIR is defined as the number of participants exposed to the intervention and experiencing a certain event divided by the total exposure duration of all participants who are at risk for the event. Specifically, for participants with no such event, the at-risk exposure duration is calculated from the Day 1 to EOT + 3 days; for participants with at least one event of a certain SOC or PT, the at-risk exposure duration is calculated from Day 1 to the first onset of such event.
- The TE-AE summaries above will also be reported for subgroups by PAH medication at baseline - Group 1 (defined in Section 5.6.8).
- TE-Serious AEs will also be summarized, by SOC and PT. In addition, serious TE-AEs will be summarized for subgroups by PAH medication at baseline - Group 1 (defined in Section 5.6.8).
- TE- AEs leading to discontinuation of study intervention will also be summarized, by SOC and PT. In addition, they will be summarized for subgroups by PAH medication at baseline - Group 1 (defined in Section 5.6.8).
- Severe TE-AE will also be summarized, by SOC and PT. In addition, severe TE-AEs will be summarized for subgroups by PAH medication at baseline - Group 1 (defined in Section 5.6.8).
- Related TE-AE will also be summarized, by SOC and PT. In addition, related TE-AEs will be summarized for subgroups by PAH medication at baseline - Group 1 (defined in Section 5.6.8).
- TE- AEs leading to fatal outcome will also be summarized, by SOC and PT. In addition, they will be summarized for subgroups by PAH medication at baseline - Group 1 (defined in Section 5.6.8).
- TE-Serious AEs associated with COVID-19 infection will also be summarized, by PT. The summary will report data from OLS only.
- TE-AEs associated with COVID-19 infection leading to death will be summarized too, by PT and for OLS only.

Listings of all AEs, SAEs and AEs with fatal outcome will be generated, separately, for STS (A302+A303) and OLS.

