3.4.2 Patient's follow-up after study drug discontinuation

An EOS visit must be performed [Section 3.10.4] after permanent discontinuation of the study drug. It is recommended to perform the EOS visit within 7 days of the last study drug intake. The patient will be followed for 30 days after the permanent study drug discontinuation to collect information on SAEs. If discontinuation is considered study drug-related, the patient will remain under the supervision of the investigator until satisfactory health has returned.

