4 SAFETY DEFINITIONS AND REPORTING REQUIREMENTS

4.1 Summary table

Periods	Treatment	Follow-up	After follow-up
Timeframe	During study drug administration and until 3 days after last study drug administration	From 3 days to 30 days after study drug discontinuation	After 30 days
AE/SAE reporting on CRF AE page	All AEs/SAEs (treatment-emergent ¹)	None	None
SAE reporting on SAE form	All SAEs (treatment-emergent ¹)	All SAEs	If felt appropriate by investigator
Final study report	Analyzed	Described	Might be described

¹A treatment-emergent AE is any AE temporally associated with the use of study drug (from study drug initiation until 3 days after study drug discontinuation), whether or not considered related to the study drug.

The resolution date and outcome of AEs reported during the double-blind study AC-065A302/GRIPHON that are ongoing at the time of the patient's Visit 1 in AC-065A303/GRIPHON OL, must be recorded on specific CRF pages (Ongoing AEs from the GRIPHON study). If the AE worsens (i.e., changes intensity, seriousness or relationship) during AC-065A303/GRIPHON OL, a new AE must be recorded on the standard AE pages with the onset date equal to the date of worsening.

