4.2.4 Reporting of adverse events

All AEs occurring after study drug initiation and up to 3 days after study drug discontinuation must be recorded on specific AE pages of the CRF.

All AEs ongoing from the AC-065A302/GRIPHON study must be reported on the dedicated AC-065A303/GRIPHON OL CRF pages and outcome must be reported when it is known.

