4.3.2.2 Treatment period

All SAEs, regardless of causal relationship, must be reported, including those related to study-mandated procedures. Those SAEs occurring during study drug administration, i.e., between study drug initiation and three days after study drug discontinuation, are defined as treatment-emergent SAEs.

These SAEs are reported on SAE forms and also on AE pages in the CRF. They are therefore entered into both the drug safety and clinical databases, and must be reconciled before study closure.

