4.3.2.3 Follow-up period

All SAEs regardless of causal relationship occurring from 3 days after study drug discontinuation until 30 days after study drug discontinuation must be reported.

All SAEs occurring during the follow-up period must be recorded on an SAE form. These SAEs are therefore entered only into the drug safety database.

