4.3.2.4 Reporting procedures

All new SAEs as well as new information regarding SAEs ongoing from the AC-065A302/GRIPHON study must be reported by the investigator to the Actelion drug safety department within 24 hours of the investigator's first knowledge of the event.

All SAEs must be recorded on SAE forms, irrespective of the study drug received by the patient, and whether or not this event is considered by the investigator to be related to study drug. These SAE forms must be faxed to the Actelion drug safety department (contact details for which are provided at the beginning of this protocol). The investigator must complete the SAE form in English (unless otherwise specified), and must assess the relationship of the event to study drug.

Such preliminary reports will be followed by detailed descriptions that may include copies of hospital case reports, autopsy reports, hospital discharge summaries and other documents when requested and applicable. Follow-up information about a previously reported SAE must also be reported within 24 hours of receiving it. The Actelion drug safety department may contact the investigator to obtain further information.

Suspected (considered related to the study drug) Unexpected (not previously described in the reference safety document) Serious Adverse Reactions (SUSARs) will be expedited by Actelion to Health Authorities, ECs/IRBs and investigators, as appropriate.

The reference safety document to assess expectedness of a suspected serious adverse reaction and need for reporting by the sponsor to regulatory authorities, ECs/IRBs, and investigators is the Investigator's Brochure [[Selexipag IB](#), section 6 Reference Safety Information].

The following events are anticipated to occur in subjects with PAH, and will be considered as 'disease-related': signs and symptoms of PAH worsening/exacerbation/progression, abdominal pain, anorexia, chest pain, cyanosis, diaphoresis, dizziness, pre-syncope, syncope, dyspnea, orthopnea, fatigue, hemoptysis, heart failure, hypoxia, palpitations, collapse, systemic arterial hypotension, and tachycardia. These events therefore do not require expedited reporting to Health Authorities, ECs/IRBs, and investigators. Like all other SAEs, these SAEs must be reported on an SAE form by the investigator to the Actelion drug safety department within 24 hours of the investigator's first knowledge of the event, and be reported on the AE page of the CRF.

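### The SAE table through EOT + 30 days is built from CRF AE pages, which A303 requires only to EOT + 3 days

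*SAP*

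**What the plan says.** SAP 5.5.2 defines the adverse events to be analysed as "Any events recorded on the AE pages of the A303 CRF or A302 CRF". SAP 1 gives the source data as SDTM data sets supplied by clinical data management. SAP 5.5.2.1 then lists, as an outcome category separate from the treatment-emergent SAEs, "All SAEs occurring at or after the initial administration of study intervention through EOT plus 30 days", and contrasts this window with the 3-day one. The category is reported for both OLS and STS, and the same section plans listings of SAEs and of fatal AEs. The SAP does not mention the drug safety database, and Appendix 2 (changes to protocol-planned analyses) lists neither this summary nor an import of safety-database records.

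The protocol routes SAEs by period:

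- **Treatment period (4.3.2.2), to 3 days after discontinuation.** SAEs go on SAE forms and on AE pages: "They are therefore entered into both the drug safety and clinical databases, and must be reconciled before study closure".
- **Follow-up period (4.3.2.3), from 3 to 30 days.** SAEs go on an SAE form: "These SAEs are therefore entered only into the drug safety database".
- **AE pages (4.2.4).** AEs after study drug initiation and "up to 3 days after study drug discontinuation must be recorded on specific AE pages of the CRF".
- **Summary table (4.1).** The row "AE/SAE reporting on CRF AE page" reads none for the follow-up period. The row for the final report has treatment-period events analysed and follow-up events described.

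One sentence in 4.3.2.4 points the other way. It says disease-related SAEs, in the same way as other SAEs, must go on an SAE form "and be reported on the AE page of the CRF", and it states no period.

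**The concern.** The SAP's analysis window is 30 days, but the source it names is required for only the first 3 of those days. Long-term safety and tolerability is the study's only objective, and protocol 3.4.2 gives the purpose of the extra follow-up: "The patient will be followed for 30 days after the permanent study drug discontinuation to collect information on SAEs".

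Because the SAP sets the EOT + 30 category against the EOT + 3 category, a reader is likely to take the gap between the two tables as the SAE burden after stopping. As written, that gap depends on which database an event was entered in. A near-zero difference could reflect routing rather than absence of events, and would be falsely reassuring.

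The listings share the problem. A death in the follow-up window could appear in the death tables with no matching entry in the SAE or fatal-AE listing if the causal event began after EOT + 3. Non-fatal SAEs with onset on days 4 to 30 would be absent from the SAE listing on the same reasoning.

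**Working it through.** The plan states no figure to reproduce: SAP 2 and 3 give hypotheses and sample size as not applicable. The check compares collection rules with analysis rules, then sizes the uncovered window.

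**Rules by onset time in A303**

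| Onset | SAE form | CRF AE page (4.1, 4.2.4, 4.3.2.2, 4.3.2.3) | In SAP EOT + 30 window |
|---|---|---|---|
| Day 1 to EOT + 3 | Yes | Yes, reconciled | Yes |
| EOT + 4 to EOT + 30 | Yes | No, safety database only | Yes |

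The protocol's two periods meet at day 3; day 3 is counted here as covered. An event that began by EOT + 3 and continued is on the AE page and is followed (4.2.5, 4.3.3), so only new onsets are at issue.

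**Inputs.** Group sizes are from the table layout in SAP 4: ex-selexipag 330, ex-placebo 379, total A303 709, selexipag in A302 574, all 953. They are consistent: 330 + 379 = 709 and 574 + 379 = 953.

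**Uncovered window.** 30 − 3 = 27 days, and 27/30 = 90% of the post-treatment window.

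**Ceiling on uncovered follow-up in OLS**

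- Total: 709 × 27 = 19,143 person-days; 19,143/365.25 = 52.4 person-years
- Ex-selexipag: 330 × 27/365.25 = 24.4
- Ex-placebo: 379 × 27/365.25 = 28.0

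This is a ceiling. It assumes that all 709 were alive and followed to day 30, and some data from participants in China are not collected or are excluded (SAP 1).

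**Share of STS governed by the A303 rules.** SAP 5.1.3.2 sets EOT at the later of the last A302 or A303 selexipag dose.

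- All: 709/953 = 74.4%
- Selexipag in A302: 330/574 = 57.5%
- Selexipag in A302 only: 574 − 330 = 953 − 709 = 244 participants. A302's collection rules are not in the documents, so this part is not judged.

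**Event count.** None can be derived, because the documents give no A303 SAE rate. As illustration only, assumed rates of 0.1, 0.25, 0.5 and 1.0 SAEs per person-year over 52.4 person-years give about 5, 13, 26 and 52 events. If half the follow-up was obtained, these halve. If sites applied 4.3.2.4 to follow-up SAEs, the shortfall is smaller and possibly nil.

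**The case against.** The strongest reply is that incompleteness is not proven. Protocol 4.3.2.4 is a general procedures section and can be read as putting every SAE, in any period, on the AE page. If all sites worked that way, the table could be complete. This stands as a limit on size. It does not remove the mismatch, because 4.1 and 4.3.2.3 address the follow-up period specifically and say the opposite. If only some sites followed 4.3.2.4, the table holds an uneven subset, which is harder to interpret than a clean omission.

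Second, SAP 5.5.2 does not contain the word only, and the SDTM might include safety-database records. The CRF specifications that could help settle this are not available. The plain reading of 5.5.2 still limits events to AE pages. If an import is intended, one sentence would say so.

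Third, 90% describes the post-treatment window, not the whole table. The table runs from Day 1 to EOT + 30. For assumed treatment of 1 to 5 years, 27 days is about 6.8% (27/395.25) down to 1.5% (27/1,856.25) of that span. The table also counts participants with at least one occurrence, so a repeat of the same preferred term adds nothing. This is fair for the table's overall percentages. It does not help the comparison between the two windows, which rests on the last 27 days.

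Fourth, the consequences are limited. SAP 5.5.2.4 takes deaths from the Study completion page and also tabulates their causes, and protocol 4.1 has follow-up SAEs described in the report. Both points stand: the events are not lost, and the main gap is in non-fatal SAEs. But the SAP does not link that description to this table.

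**Conclusion.** The concern holds. For OLS and the A303 part of STS, the table labelled through EOT + 30 days rests on a source that the protocol's period-specific rules do not require for days 4 to 30. Those days make up 27 of 30 post-treatment days and at most 52.4 person-years in OLS. The A303 rules govern this window for 74.4% of the STS All column and 57.5% of the selexipag-in-A302 column.

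Confidence is high for the mismatch in the text. There is none to be had on the number of SAEs missing, which the documents do not settle. The conclusion assumes that SAP 5.5.2 means what it says about AE pages, and that the specific follow-up rules prevail over the general sentence in 4.3.2.4.

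The effect is confined to one descriptive table and the SAE and fatal-AE listings. The protocol endpoints to EOT + 3, the treatment-emergent tables and the death counts do not change. It should be fixed, because the table as specified claims a window its source need not cover.

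**What to change.** Amend SAP 5.5.2 and 5.5.2.1 in one of two ways.

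1. **Limit the claim.** Label the A303 EOT + 30 SAE table as restricted to AE-page collection, or drop it for A303, and describe follow-up SAEs separately as protocol 4.1 provides. This costs wording only.
2. **Complete the table.** State that A303 SAEs with onset after EOT + 3 and up to EOT + 30 days are taken from the drug safety database, coded in MedDRA 22.0 and reconciled with AE-page records and with deaths on the Study completion page. They are then added to the table and to the SAE and fatal-AE listings. This costs one extract, coding and a further reconciliation, because protocol 4.3.2.2 requires reconciliation only for treatment-period SAEs. The effort cannot be judged from the documents.

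In either case, record how protocol 4.3.2.4 is reconciled with 4.1, 4.2.4 and 4.3.2.3. That contradiction lies inside the protocol, but the SAP should state which rule its source data follow. Neither option needs new data collection.

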3.8.2 Safety and tolerability endpoints

- Treatment-emergent AEs up to 3 days after study drug discontinuation.
- Treatment-emergent SAEs up to 3 days after study drug discontinuation.
- AEs leading to permanent discontinuation of study drug.

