5.1.3. Study Day 1 and End of Treatment

5.1.3.1. For Treated Set - OL

Study Day 1 (or Day 1) refers to the start date of the first study intervention administration in A303, as defined in Section 4. If the start date is missing, the date of Visit 1 in CRF will be used.

End of treatment (EOT) refers to the date of the last selexipag administration in A303.

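### The SAP limits the discontinuation endpoint to treatment-emergent AEs without declaring it, so an unchanged A302 AE that ends selexipag in A303 is not counted in OLS, nor in STS for ex-placebo participants

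*SAP*

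**What the plan says.** Protocol 3.8.2 lists three safety and tolerability endpoints. The first two carry a treatment-emergent window; the first reads "Treatment-emergent AEs up to 3 days after study drug discontinuation". The third reads "AEs leading to permanent discontinuation of study drug", with no such window.

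SAP 5.5.2.1 turns the third endpoint into "TE-AEs leading to discontinuation of study intervention", identified by the CRF tick box that records a permanent stop as the action taken. Treatment-emergent is defined there as "Any AE occurring at or after the initial administration of study intervention (on Day 1 in STS [A302+A303] or OLS", running to EOT plus 3 days. For OLS, SAP 5.1.3.1 states: "Study Day 1 (or Day 1) refers to the start date of the first study intervention administration in A303". For STS, SAP 5.1.3.2 sets Day 1 at the first selexipag dose in either study, whichever came earlier.

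For AEs still open when a patient enters A303, Protocol 4.1 has resolution date and outcome recorded on separate pages. It adds: "If the AE worsens (i.e., changes intensity, seriousness or relationship) during AC-065A303/GRIPHON OL, a new AE must be recorded". Stopping the drug is not among the triggers for a new record.

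SAP Appendix 2, which lists departures from the protocol's planned analyses, does not mention the added treatment-emergent limit.

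**The concern.** Long-term safety and tolerability is the study's only objective, and this is one of its three endpoints. A patient who enters A303 with a persistent side effect and eventually gives up selexipag because of it, with no change in grade, seriousness or causality, is a tolerability failure in A303. Under the SAP rule that AE keeps its A302 onset date and falls outside the OLS window.

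The error can go in only one direction, because adding an onset condition can remove cases but never add them. The CSR could also show a count of AE-related stops in the AE table that differs from the one in the disposition table, with no planned explanation. SAP 5.5.2.2 applies the same treatment-emergent limit to AESIs leading to discontinuation, and SAP 5.5.2.3 reuses it for prostacyclin associated reactions.

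**Working it through.** **Inputs.** SAP Section 4 gives the group sizes: ex-selexipag 330, ex-placebo 379, OLS 709, selexipag in A302 574, STS 953. These are consistent: 330 + 379 = 709 and 574 + 379 = 953. The plan has no hypothesis, power or sample-size figure to reproduce for this point.

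**Rule.** An AE is treatment-emergent in a set if Day 1 of that set ≤ onset ≤ EOT + 3 days. Reading the SAP's word occurring as onset is an inference. It is supported by Protocol 5.2.2.1, which defines treatment-emergent AEs by onset.

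**Rule applied to an A302 AE (onset after the first A302 dose) that leads to stopping selexipag in A303:**

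| Prior arm | Course in A303 | Treatment-emergent in OLS | Treatment-emergent in STS |
|---|---|---|---|
| Ex-selexipag | Unchanged | No: onset before first A303 dose | Yes: onset after first A302 selexipag dose |
| Ex-placebo | Unchanged | No | No: Day 1 is the first A303 dose here too |
| Either | Worsened, new record at worsening date | Yes | Yes |

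The upper limit of EOT + 3 days removes nothing, because an AE that causes the stop began before it.

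**The STS entry for ex-selexipag participants.** The date condition is met, but the count also needs the action-taken tick. Protocol 4.1 and 4.2.4 describe the ongoing-AE pages as holding resolution date and outcome, and do not mention action taken. SAP 5.5.2 draws on the AE pages of the two CRFs without saying whether the ongoing-AE pages are included. The CRF is not among the documents, so capture here is uncertain.

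**Size.** The number of such cases, k, is not in the documents. If all k fall in the column shown, the proportion is understated by 100 × k / n percentage points:

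| k (assumed) | Ex-selexipag, n = 330 | Ex-placebo, n = 379 | OLS total, n = 709 | STS all, n = 953 (ex-placebo cases) |
|---|---|---|---|---|
| 1 | 0.30 | 0.26 | 0.14 | 0.10 |
| 5 | 1.52 | 1.32 | 0.71 | 0.52 |
| 10 | 3.03 | 2.64 | 1.41 | 1.05 |

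By date, the STS loss can concern only the 379 ex-placebo participants, who are 379 / 953 = 39.8% of that set.

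**The case against.** The strongest defence starts from the protocol's own analysis population. Protocol 5.1 specifies all patients who started selexipag in either study, which is the SAP's STS. There, an AE that began on selexipag in A302 is treatment-emergent, so for ex-selexipag participants the date rule removes nothing. OLS is a set the SAP adds to show A303 alone, and presenting the two side by side is a sensible way to handle carry-over.

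For OLS itself, Protocol 4.2.1 does not regard a pre-existing condition that has not worsened as an AE, and the standard A303 AE pages collect events after study drug initiation. The SAP wording therefore partly follows the data collection. The case is also narrow: an AE troublesome enough to end treatment may well be regraded, and it is then re-recorded and counted in both sets. Finally, the stop is not hidden. SAP 5.2 tabulates reasons for discontinuation and lists premature stops for both sets, and SAP 5.5.2.1 provides listings of all AEs.

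Most of this stands, and it limits the point. It does not remove it. OLS columns will be reported for a protocol endpoint that has no onset limit. Protocol 4.2.4 requires the carried-over AEs to be reported on A303 pages, so they are not outside the study's data. Disposition gives a reason for stopping but no SOC or PT, and no reconciliation with the AE table is planned. Ex-placebo cases are lost in STS as well.

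**Conclusion.** The point holds as a limited, undeclared narrowing of a protocol endpoint. Unchanged A302-onset AEs that end selexipag in A303 are omitted from the discontinuation count in both OLS columns and, for ex-placebo participants, in STS. This rests on reading the SAP's treatment-emergent rule by onset date. The size is unknown and probably small: 0.30 points per case among 330 ex-selexipag participants and 0.26 points per case among 379 ex-placebo participants.

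Three stronger readings are tempting, and the documents do not support them:

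- **That such events vanish from the endpoint altogether.** In STS the ex-selexipag case qualifies by date. Whether it is nevertheless missed depends on a CRF that is not shown.
- **That the undercount falls mainly on the ex-selexipag column.** In OLS the rule affects both columns, and in STS the date rule affects only ex-placebo participants.
- **That a relative undercount can be stated.** This would need the share of participants entering with an ongoing AE, the share who stop for it unchanged, and the overall AE-discontinuation rate. None of these is given.

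**What to change.** In SAP 5.5.2.1, count any AE recorded as leading to permanent discontinuation of selexipag in A303, whatever its onset date, and state that AEs on the ongoing-AE pages are included. Keep the treatment-emergent subset as now defined. In OLS, show A302-onset cases on a separate line split by prior arm, so that AEs that began on placebo can be identified.

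Check the total against the disposition reason for stopping. Where a stop is attributed to an AE but cannot be linked to an AE record, report it as *AE, term not linked* rather than assigning a SOC or PT afterwards. This also covers the possibility that the ongoing-AE pages lack action taken. List the change in Appendix 2.

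The cost is a wording change and one reconciliation step against data the SAP already tabulates. The discontinuation figure may become slightly less favourable.
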